8.1 Analysis Sets

- *Modified Intent-To-Treat (mITT)*: all randomized participants who receive IP in at least one blinded Experimental Session (Visit 5) and have at least one follow-up CAPS-5 assessment post-treatment
- *Per Protocol (PP)*: all randomized participants who meet eligibility criteria, who receive IP in three Experimental Sessions, and have three follow-up CAPS-5 assessments post-treatment
- *Not Per Protocol (NPP)*: all participants who are included in the *mITT* set but not the PP set
- *Safety*: all participants who receive any IP
- *All Enrolled*: all participants who sign informed consent and are initially enrolled

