8.3.4 Independent Rater Assessments

Participants will have two CAPS-5 assessments during the treatment period of the study (Visits 8 and 13). A blinded IR from the IR Pool will conduct the assessments via telemedicine. These assessments may be recorded to establish inter-rater reliability. The results will not be sent to site staff but instead will be sent to a blinded IR Coordinator to enter the data which will be blinded to sponsor and site personnel. Participants will be instructed to withhold their opinion on treatment group assignment or the number of study visits they have completed from IRs. The IR will also administer the DSP-I and SDS at these time points.

An Integrative Session and CAPS-5 assessment may take place on the same day (in the appropriate order, per protocol). The assessments will be scheduled as follows:

- CAPS-5 T2 (Visit 8): 18 to 30 days after Experimental Session 1 (Visit 5), between Integrative Session 1.2 (Visit 7) and Integrative Session 1.3 (Visit 9)
- CAPS-5 T3 (Visit 13): 18 to 30 days after Experimental Session 2 (Visit 10), between Integrative Session 2.2 (Visit 12) and Integrative Session 2.3 (Visit 14).

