Record																
All AEs A																
Randomization B																
Container Assignment B																
Administer IMP																
8-hour Exp. Session																
BP, Pulse, Temperature C																 D
Overnight Stay																
90-min Integrative Session																
Phone Call Follow-up E																
Weight																

- A All Adverse Events (AEs) includes collecting Serious Adverse Events, AEs of Special Interest, AEs of Psychiatric Status, AEs requiring medical advice or attention, AEs that indicate withdrawal of a participant, and all other AEs
- B Randomize 24 to 48 hours prior to first Experimental Session; obtain container assignment 24 to 48 hours prior to each Experimental Session
- C During Experimental Sessions, vitals are measured before Investigational Product administration, immediately before the supplemental dose is administered (or would be, if supplemental dose not given), and approximately 8 hours after initial dose, and as needed
- D At Study Termination, only blood pressure needs to be measured

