where, the CAPS variable is the change from baseline in the CAPS-5 total severity score at each visit, the ID variable uniquely identifies the participant, Baseline_CAPS is the baseline CAPS-5 Total Severity Score for each participant, DS is the dummy variable indicating dissociative subtype at baseline, and Site indicates the clinical site where the participant was treated. There is a record for each visit for every participant. If the unstructured variance/covariance model assumption doesn't allow the REML algorithm to converge, a heterogeneous Toeplitz structure will be used. If the model doesn't converge under heterogeneous Toeplitz, the homogeneous Toeplitz structure will be used. If that fails to converge, the next variance/covariance attempted will be AR(1). In the event AR(1) structure fails to converge, the compound symmetry assumption will be used.

Table 4: Proposed Estimands and Key Attributes

Estimand	Hypothesis	Inference	Population	Endpoint	Use of data after early termination in analysis
1	de jure	Initially randomized treatment	mITT	Planned endpoint	Not included
2	de facto	Treatment Policy	mITT	Planned endpoint	Included

8.7.2 Supportive Analyses:

To support the need to provide information on treatment effectiveness in all randomized participants that could be expected in clinical practice, regardless of adherence to the 3-session

course of MDMA-assisted psychotherapy treatment, we propose a *de facto* estimand is included as an exploratory supportive analysis (Estimand 2 in [Table 4](#)).

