The *de facto* estimand will include all available CAPS-5 outcome data from all participants in the mITT set regardless of adherence to the treatment, including CAPS-5 data collected after treatment discontinuation in case of early termination. This will be estimated in the mITT set by a statistical comparison between treatment groups using the MMRM model with a weighted least squares estimate of the change in CAPS-5 scores from baseline to 18 weeks after randomization across all the post treatment CAPS-5 measures. The sponsor expects no more than 5% of the participants will discontinue treatment after the first experimental session and CAPS-5 outcome assessment, due to the highly-controlled treatment setting which is analogous to residential or in-patient treatment settings. Additionally, some participants may choose to discontinue after the first experimental session because of strong and early positive response. These participants are treatment successes and should not be modeled as treatment failures. Using the least squares estimate of the mean reduction in CAPS-5 scores across all treatment sessions will capture these early successes in the *de facto* estimand. It can be argued that because all participants in the study will have continued data collection and all observed post-treatment CAPS-5 scores included in the *de facto* estimand that there is no missing data in this analysis. Thus the *de facto* estimand will support the primary *de jure* estimand.

1. The choice of primary estimand will be tested with a supportive analysis including a different estimand:
 - a. To determine *de facto* effectiveness by comparing MDMA-assisted psychotherapy to identical psychotherapy with inactive placebo for PTSD, as measured by the estimand of change in CAPS-5 Total Severity Score from Baseline after 18 weeks post-randomization, including all observed data after early termination.
2. The effect of departures from choices and assumptions made for the primary analysis will be tested as sensitivity analyses for the primary estimand. No sensitivity analyses will be performed for the secondary efficacy endpoints. Details of the sensitivity analyses with multiple imputation will be provided in the Final SAP.
 - a. Distributional assumptions for the full data will be tested, if distribution found not to be normal, we will test a transformation of the data, such as the log transformation, to achieve normality.

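### The treatment-policy analysis is presented as covering all randomized participants but is run in mITT, which omits anyone never dosed or never reassessed

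*SAP*

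**What the plan says.** SAP 8.7.2 gives the purpose of the de facto estimand as supplying "information on treatment effectiveness in all randomized participants that could be expected in clinical practice", whether or not participants complete the three sessions. Table 4 labels it treatment policy and gives its population as mITT. The text repeats that it "will include all available CAPS-5 outcome data from all participants in the mITT set regardless of adherence to the treatment".

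SAP 8.1 sets two conditions for mITT beyond randomization: IP in at least one blinded Experimental Session, and that participants "have at least one follow-up CAPS-5 assessment post-treatment". Protocol 5.3.1 and 14.2 define the set in substantially the same way. SAP 8.7.1 bases all efficacy analyses on it.

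Two timing facts matter. The SAP's Time and Events table says "Randomize 24 to 48 hours prior to first Experimental Session", so assignment comes before dosing. Protocol 8.3.4 schedules the first follow-up CAPS-5 (Visit 8) 18 to 30 days after Session 1.

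SAP 8.7.2 also says it can be argued that the de facto analysis has no missing data. Table 5, the reference-based imputation scheme, is limited by its title to mITT and by its last column to CAPS-5 values after Session 2 or 3.

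**The concern.** A treatment-policy result is meant to describe what follows from assignment, whatever happens afterwards. Here membership depends on two events after randomization: being dosed, and supplying an outcome measurement. The comparison no longer covers everyone randomized, although the SAP offers it on that basis.

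The supportive analysis should show whether the primary result withstands early loss. Because it shares the primary population, it cannot speak to loss before any follow-up CAPS-5. The control is inactive, and Protocol 5.5 expects the active doses to produce the commonly reported effects of MDMA, so early leaving could plausibly differ between arms. SAP 8.2 continues enrollment until 100 participants are in mITT, so the analysed number will not reveal how many were left out.

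**Working it through.** **1. Who is in which analysis**

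| Situation | Safety set | mITT and de facto analysis | Table 5 imputation |
|---|---|---|---|
| Randomized, never dosed | No | No | No |
| Dosed, stops early, gives any later CAPS-5 | Yes | Yes | Yes, for later missing values |
| Dosed, withdraws or is lost, gives no CAPS-5 | Yes | No | No |

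The first and third rows are the gap. Protocol 5.3.4 frames its early-termination follow-up around people who have received IMP, so it does not clearly cover the first row. In the third row, a participant who withdraws consent gives a final CAPS-5 only by agreement.

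Table 5 shows an inconsistency. An MDMA participant who withdraws consent after a first follow-up CAPS-5 is treated as a failure and imputed by jump to reference. The same person leaving before any CAPS-5 is dropped from the analysis.

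**2. The plan's own figure**

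Inputs from SAP 7.0: final-visit mean changes of 37.4 (MDMA) and 20.5 (placebo) on CAPS-4, variances 335 and 280, 47 per group, alpha 0.0499 (two-sided per SAP 8.7.1), conversion factor 20/34.

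- Difference: 37.4 − 20.5 = 16.9. SD: √(335 + 280) = 24.80.
- Standard error: 24.80 × √(2/47) = 5.12. Ratio: 16.9 / 5.12 = 3.30.
- Power: Φ(3.30 − 1.96) ≈ 91.0% (90.5% with the noncentral t), against the stated 90%. The figure reproduces and is not in dispute.
- CAPS-5 scale: MDMA 37.4 × 20/34 = 22.00; placebo 20.5 × 20/34 = 12.06; difference 9.94.

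**3. Size of the gap (illustration)**

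The documents give no count of participants outside mITT, so the counts are assumed. Take 9.94 as the difference within mITT, and let k of 50 MDMA participants be excluded and then given the placebo mean. The difference becomes 9.94 × (1 − k/50).

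| k of 50 | Difference | Fall |
|---|---|---|
| 0 | 9.94 | 0 |
| 1 | 9.74 | 0.20 |
| 2 | 9.54 | 0.40 |
| 3 | 9.34 | 0.60 (6%) |

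Three per arm is the plan's dropout allowance for the whole study. SAP 8.2 expects up to 5% early termination (2.5 of 50), and Protocol 2.2.4 reports 7.5% Phase 2 dropout (8 of 107, about 3.7 of 50). Only part of either would fall before any CAPS-5.

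The SAP describes the de facto estimate as taken across all post-treatment assessments. With equal visit weights (assumed), the planning difference is (11.7 + 18.3 + 16.9)/3 × 20/34 = 9.20, and 3 of 50 costs 0.55 points. The conclusion does not change.

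**4. The other direction**

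If instead 3 of 50 placebo participants are lost and had zero change, restoring them lowers the placebo mean to 12.06 × 47/50 = 11.34. The difference rises to 22.00 − 11.34 = 10.66, an increase of about 0.7 points.

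**The case against.** The best defence is that the plan works to keep this group small. Under Protocol 5.3.4 and SAP 8.2, people who discontinue treatment stay on the rater schedule. Protocol 8.4.2 calls for a final CAPS-5 immediately on withdrawal from treatment, and full dropouts are asked for one. SAP 8.5 already tabulates participants by arm in the Safety and mITT sets and reports discontinuations with reasons, on a randomized denominator. Table 4 states the mITT population openly, the analysis is exploratory, and the phrase about all randomized participants occurs in a sentence of rationale. All of this stands, and it limits the size of the problem. It does not remove the mismatch or bring the omitted participants into any efficacy analysis.

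A reader might infer three stronger things, none of which the documents support:

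- **That mITT requires a CAPS-5 at least 18 days after Session 1.** SAP 8.1 sets no minimum day. The 18 to 30 days are the Visit 8 window, and a CAPS-5 taken at an earlier withdrawal would qualify.
- **That the omitted participants are early treatment failures, so the effect is inflated.** This is plausible but not shown. SAP 8.7.2 expects some people to stop because of an early good response, and leaving after guessing placebo would mainly remove placebo participants.
- **That losses could reach 5 of 50 in the MDMA arm.** Nothing in the plan points to that many before a first follow-up CAPS-5.

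**Conclusion.** The point holds as a mismatch between the stated scope of the treatment-policy analysis and its population. Participants never dosed, or dosed and never reassessed, are in no efficacy analysis, and the suggestion that the de facto analysis has no missing data does not account for them. Table 5 itself records no data after consent is withdrawn.

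The likely size is modest: a fall of 0 to 0.6 points on 9.94 if 0 to 3 of 50 MDMA participants are restored at the placebo mean, and a possible shift the other way if losses are confined to placebo. These figures rest on assumed counts, on assumed outcomes for unobserved people, and on the planning means holding within mITT. The direction cannot be settled from the documents. The primary test and its alpha are not affected by this point. The change is worth making because it removes a selection after randomization from the analysis intended to be free of it.

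**What to change.** - In SAP Table 4 and 8.7.2, set the population of Estimand 2 to all randomized participants, by assigned arm.
- Extend the Table 5 imputation to those with no post-baseline CAPS-5: jump to reference for MDMA, and imputation from the placebo arm for placebo.
- In the SAP 8.5 disposition table, add the number randomized but outside mITT, by arm and reason, separating never dosed from dosed without a CAPS-5.
- Leave the primary mITT analysis unchanged.

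If the population is kept as mITT, delete the statements that the analysis informs on all randomized participants and that it has no missing data.

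The cost is SAP wording, a little programming and a possibly slightly smaller supportive estimate. One limit should be stated in the report: this imputation gives placebo leavers placebo-like values, so it cannot show a shift caused by poor outcomes among them. The counts by arm and reason let a reader judge that.

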8.2 Missing Data Handling

All possible procedures within Good Clinical Practice (GCP) will be used to minimize Post-randomization Early Termination. Based on Phase 2 data it is expected that up to 5% of enrolled and randomized participants will terminate early. Post-randomization Early Terminators will be compared to the Completers using baseline demographics and CAPS-5 Total Severity Score at baseline. For the Post-randomization Early Terminators, data collection by IRs will continue on the same schedule as planned through Study Termination visit procedures in order to limit missing data. All observed CAPS-5 data up to the point of discontinuation of treatment will be included in the MMRM model of the *de jure* estimand from Post-randomization Early Terminators. Participants will not be replaced, enrollment and treatments will continue until N=100 participants are obtained in the *mITT* set. All observed CAPS-5 data from Post-

randomization Early Terminators collected prior to and after early termination will be included in the supportive effectiveness analysis of the *de facto* estimand.

8.2.1 Partial or Missing Dates

The following conventions will be used to impute missing portions of dates for AEs and concomitant medications. Note that the imputed values outlined here may not always provide the most conservative date. In those circumstances, the imputed value may be replaced by a date that will lead to a more conservative analysis.

Start Dates:

1. If the year is unknown, then the date will not be imputed and will be assigned a missing value.
2. If the month is unknown, then:
 - a. The month and day of the first dose date will be imputed if the year matches the first dose date year.
 - b. Otherwise, 'January' will be assigned.
3. If the day is unknown, then:
 - a. The day of the first dose date will be imputed if the month and year match the first dose date month and year.
 - b. Otherwise, the first day of the month will be assigned.

Stop Dates:

1. If the year is unknown, then the date will not be imputed and will be assigned a missing value.
2. If the month is unknown, then 'December' will be assigned.
3. If the day is unknown, then the last day of the month will be assigned.

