8.3.1 Experimental Sessions

There will be three blinded Experimental Sessions (Visits 5, 10, 15). Procedures for MDMA-assisted psychotherapy will remain the same across all sessions and all procedures regardless of dose received. Experimental Sessions must be at least 8 hours long, measured from 30 minutes prior to IMP administration.

Experimental Sessions will be scheduled as follows:

- Experimental Session 1 (Visit 5) will occur within 4 to 7 days after the Baseline CAPS-5 (Visit 3) assessment; 1 to 4 days after Preparatory Session 3 and Enrollment Confirmation (Visit 4). Experimental Session 1 (Visit 5) must occur within 7 days of the Baseline CAPS-T1 (Visit 3) and after Preparatory Session 3 and Enrollment Confirmation (Visit 4). If the Baseline CAPS-5 assessment is completed outside of the allowed window, the investigator should consult the CRA and Medical Monitor to determine if the assessment should be repeated. The first Experimental Session will include 80 mg of IMP followed by a supplemental half-dose 1.5 to 2 hours after the initial dose unless contraindicated.
- Experimental Session 2 (Visit 10) will occur 21 to 35 days after Experimental Session 1 (Visit 5) and at least 1 day after Integrative Session 1.3. A dose of 80 or 120 mg MDMA or placebo will be administered. A supplemental half-dose will be administered 1.5 to 2 hours after the initial dose unless contraindicated.
- Experimental Session 3 (Visit 15) will occur 21 to 35 days after the second Experimental Session (Visit 10) and after Integrative Session 2.3. A dose of 80 or 120 mg MDMA or placebo will be administered. A supplemental half-dose will be administered 1.5 to 2 hours after the initial dose unless contraindicated.

Table 7: Schedule of Procedures for Experimental Sessions

Approximate Time	Procedure or Action
9:30	Urine drug screen and pregnancy test, concomitant medication information collected, participant acclimated to environment, C-SSRS
9:55	Baseline BP (Blood Pressure), body temperature, pulse
10:00	IMP Administration , Begin video recording
11:30	BP, body temperature pulse Supplemental Dose Administration , unless contraindicated
17:30	C-SSRS, BP, body temperature, pulse

Pre-IMP administration

- 24 to 48 hours prior to the first Experimental Session, the participant will be randomized using a web-based randomization program.
- 24 to 48 hours prior to each Experimental Session, the site team will obtain the container assignment.

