12.0 Concomitant Medications

12.1 Tapering Instructions

The site physician will record concomitant medications during Screening. If the prospective participant is being treated with psychiatric medications at enrollment, the prospective participant will be encouraged to discuss medication tapering with their outside treating physician, if any, and will be required to give the site physician permission to do so as well. The medications will then be tapered in an appropriate fashion to avoid withdrawal effects and will be discontinued at least five half-lives plus one additional week for stabilization before the first Experimental Session to avoid the possibility of any interaction. Additionally, participants who are taking prohibited opiates will be cross-tapered to an allowable opiate (hydrocodone, morphine, and codeine) under the care of their prescribing physician.

The site physician will consult the prescribing physician to initiate medication tapering for participants, as they must refrain from taking psychiatric medications throughout the study, with some exceptions (see [Section 12.2 Allowed Concomitant Medications](#)). The prescribing physician's opinion about medication discontinuation will be documented either in writing from the prescribing physician, or in writing by the site physician documenting phone contact with the prescribing physician. Tapering will follow a time course appropriate for the medication based on its half-life, with the Baseline CAPS-5 T1 (Visit 3) scheduled to occur after complete washout (five half-lives plus at least 1 week for stabilization).

The therapy team will request information about any changes in medication at each contact. The site physician will be responsible for reviewing and confirming all medications collected during the study.

All medications, non-prescription and prescription, will be collected from Screening through 7 days after the last Experimental Session. From 7 days after the last Experimental Session through Study Termination, only prescription or non-prescription medications taken to treat AEs will be collected. Throughout the protocol, all medications used to treat AEs will be collected, and all changes including discontinuations or additions to medications will be collected. The study team will also inquire about concomitant medication adherence and document all information on the Concomitant Medications eCRF.

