8.8.3 Concomitant Medications

A secondary measure of safety will be the reporting of concomitant medications. All concomitant medications collected from Screening to Study Termination will be categorized as follows:

- Pretreatment medications are defined as medications taken prior to and after signing informed consent and those taken during the Preparatory Period prior to the first Experimental Session. A stop date is expected prior to the first Experimental Session for any medications requiring a change in dose, a skipped dose, or tapering.
- Treatment Period concomitant medications are defined as those taken or continued during the Treatment Period from the first Experimental Session to the last Integrative Session. A stop date is expected prior to the each Experimental Session for any medications requiring a change in dose, a skipped dose, or tapering.
- Concomitant medications with a start date of the day of and two days after IP administration
- Follow-up Period concomitant medications are defined as those taken or continued during the Follow-up Period after the last Integrative Session through Termination
- Any concomitant medications that are tapered
- Any concomitant medications that are taken to treat an AE
- Any concomitant medications that are taken to treat an SAE
- Any excluded concomitant medications taken as a deviation from the protocol.

Concomitant medications on case report forms will be classified using the WHO Drug Dictionary Enhanced™ (WHO DDE). Frequency and incidence of concomitant medications will be displayed by generic name, sorted by class, and summarized by treatment group, analysis set, and category as defined above. Concomitant medications will be analyzed and presented as follows:

- Concomitant medications taken on the day of and two days after IP administration will be presented separately
- Any psychiatric concomitant medications by period.

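### The partial-date rule in SAP 8.2.1 sets a start date to the first dose without checking the stop date, so a drug stopped before Session 1 can be tabulated as started on the day of dosing

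*SAP*

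**What the plan says.** SAP 8.2.1 opens with its scope: "The following conventions will be used to impute missing portions of dates for AEs and concomitant medications". For start dates it then has two branches that lead to the first dose:

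- Month unknown: "The month and day of the first dose date will be imputed if the year matches the first dose date year". Otherwise January is assigned.
- Day unknown: "The day of the first dose date will be imputed if the month and year match the first dose date month and year". Otherwise the first of the month is assigned.

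Stop dates are handled separately: "If the month is unknown, then 'December' will be assigned", and an unknown day becomes the last day of the month. No line links the start rule to the stop rule. The section admits that its dates may not always be the most conservative, and adds: "In those circumstances, the imputed value may be replaced by a date that will lead to a more conservative analysis".

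SAP 8.8.3 defines a separately presented group as "Concomitant medications with a start date of the day of and two days after IP administration". The same section expects drugs that need tapering to have a stop date before the first Experimental Session.

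On timing, Protocol 12.1 has the Baseline CAPS-5 "scheduled to occur after complete washout (five half-lives plus at least 1 week for stabilization", and Protocol 8.3.1 says "Experimental Session 1 (Visit 5) will occur within 4 to 7 days after the Baseline CAPS-5 (Visit 3) assessment". Protocol 12.1 also states the washout a second way, as five half-lives plus one week before the first Experimental Session.

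**The concern.** Setting an unknown start to the first dose date is a common and cautious convention for a record that is ongoing or stops after dosing. It is wrong for a record already known to have stopped before dosing. This trial is designed to produce such records, because psychiatric drugs are tapered after enrollment and must be gone before Session 1.

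Two safety outputs are exposed. The first is the table of medications around each dosing day, which serves safety objective 8. The second is the treatment-emergent adverse event tables. Adverse event collection starts at Enrollment (Visit 0), so events during the taper are in the dataset. Under Protocol 11.1 the investigator's opinion on causality is collected only for serious events. SAP 8.8.2 instead infers relationship from an at least two-fold difference in treatment-emergent incidence between MDMA and placebo. An event moved from before dosing to Day 0 therefore enters the comparison on which relationship is judged.

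**Working it through.** The documents give no figure to reproduce. The check applies the written rule to the protocol's own timing.

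**Inputs**

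- First dose date *F*; known stop date *S* = *F* − *G*, where *G* is the gap from stop to first dose.
- Washout before Visit 3: five half-lives plus 7 days (Protocol 5.1 Table 1 and 12.1).
- Visit 3 to Session 1: 4 to 7 days (Protocol 8.3.1).
- Alternative anchor: five half-lives plus 7 days before Session 1 (Protocol 12.1).

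**Step 1, the gap.** With half-life *h*:

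- Visit 3 anchor: *G* ≥ 5*h* + 7 + 4 = 5*h* + 11 days.
- Session 1 anchor: *G* ≥ 5*h* + 7 days.

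**Step 2, the imputed start.** If the month is unknown and the year matches, or the day is unknown and the month and year match, the imputed start is *F*. Then start − stop = *F* − (*F* − *G*) = *G*, which is positive under either anchor. Because the start equals *F*, it always lies within *F* to *F* + 2, the window used in SAP 8.8.3.

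**Step 3, an example with assumed dates.** Start 2019 with month unknown, stop 20 August 2019, first dose 16 September 2019. The imputed start is 16 September. The gap is 11 days left in August plus 16 in September = 27 days after the stop. With a stop-date check the start becomes 1 January 2019.

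**Step 4, enumeration.** The rule was coded literally for all 365 first-dose dates in one year and every true start on or before the stop, in the same year (month unknown) or the same month (day unknown). For month unknown the number of cases is *m*(*m* + 1)/2 with *m* = 365 − *G*.

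| Gap *G* (days) | Cases, month unknown | Cases, day unknown | Start after stop | In Session 1 window | Either fault with stop check |
|---|---|---|---|---|---|
| 7 | 358 × 359 / 2 = 64,261 | 3,435 | 100% | 100% | 0 |
| 11 | 354 × 355 / 2 = 62,835 | 2,383 | 100% | 100% | 0 |
| 14 | 351 × 352 / 2 = 61,776 | 1,720 | 100% | 100% | 0 |
| 56 | 309 × 310 / 2 = 47,895 | none possible | 100% | 100% | 0 |

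These are enumerated date combinations, not expected records. They show that the result is certain once a record meets the trigger. They say nothing about how often that happens.

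**Step 5, what is not touched.** A start year before the first-dose year gives January of that year. A known month other than the first-dose month gives the first of that month. An unknown year is left missing. Complete dates are not changed.

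**Step 6, the relationship rule.** Take hypothetical counts in arms of equal size. 8 against 4 gives a ratio of 2.0 and meets the two-fold threshold. One misplaced event in each arm gives 9 against 5, a ratio of 1.8, which does not. Each addition counts only if that participant has no other treatment-emergent event with the same preferred term, since SAP 8.8.2 reports each term once per participant.

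**The case against.** The best defence is that such records will be rare and easy to see. The taper is planned at Visit 0, followed through the Preparatory Sessions and confirmed by a call where needed. Medication changes are asked about at each contact, and adverse events are recorded prospectively. Medical records and prescriber contact help to fill in start dates. SAP 8.8.3 gives tapered drugs a category of their own, so a start later than a stop should stand out. The rule is the same in both arms and the medication tables are descriptive. All of this stands, and it bears on how many records are affected. It does not make the written rule correct for any of them.

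The replacement clause does not settle the matter either. It is optional, has no trigger, does not mention stop dates and does not define conservative. For a safety table, a programmer could take the dosing-day date to be the conservative one.

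Four stronger readings are tempting but go beyond the documents:

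- *The drug also becomes a Treatment Period psychiatric medication, so safety objective 9 is corrupted.* SAP 8.8.3 defines that category by drugs taken or continued in the period. A drug with a known earlier stop was neither. Only the dosing-day category is defined by start date.
- *Long-standing drugs, or drugs stopped before the trial, are generally swept in.* Tapering takes place after enrollment, and starts in earlier years are not moved to first dose.
- *Any event during the taper becomes treatment-emergent.* That requires a partial start date in the first-dose year or month.
- *The December rule is an equal, separate fault for tapered drugs.* It requires an unknown stop for a taper that the trial itself supervises. It deserves a cap, but it is a remote case.

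**Conclusion.** The point holds as a rule that gives a wrong result when followed as written. For a record with a stop before first dose and a partial start in the first-dose year (month unknown) or month (day unknown), the imputed start always falls after the stop and always in the Session 1 window. For tapered drugs the discrepancy is at least 7 days plus five half-lives under the Session 1 anchor, or 11 days plus five half-lives under the Visit 3 anchor. Those two washout statements should be reconciled, but the conclusion is the same under either.

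The reach is limited to the dosing-day medication table (safety objective 8) and, for adverse events, the Day 0 and treatment-emergent tables and the relationship rule. The CAPS-5 and SDS analyses are not affected. The documents give no rate of partial dates, so the number of records cannot be derived; it may be small or nil. The conclusion assumes that the rule is programmed literally and that the replacement clause is not used. The matter should be put right before database lock. It does not threaten the trial's main conclusions.

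**What to change.** Amend SAP 8.2.1 as follows:

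1. Use the first dose date for a partial start only when the record is ongoing, has no known stop, or has a known or partly known stop that can fall on or after first dose.
2. Otherwise impute the earliest date consistent with the known parts, never later than the stop date. For adverse events, the date should also be no earlier than Enrollment (Visit 0), because collection begins there and a default of 1 January could precede it.
3. Cap imputed stop dates at Study Termination, or at the documented end of taper where one is recorded. Derive the stop before the start, so that the check uses the capped value.

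A listing of records whose imputed start was changed by the check would show how many there are. The cost is a few sentences in the SAP and a few lines of derivation code. No new data are needed.
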